## I. LIST OF ABBREVIATIONS

CARTChimeric Antigen receptor T-Cell therapyCIChief InvestigatorCNORISClinical Negligence and Other Risks Insurance SchemeDMTData Management TeameCRFCase Report FormGCPGood Clinical PracticeGDPRGeneral Data Protection RegulationICFInformed Consent Form	
CNORISClinical Negligence and Other Risks Insurance SchemeDMTData Management TeameCRFCase Report FormGCPGood Clinical PracticeGDPRGeneral Data Protection Regulation	
DMTData Management TeameCRFCase Report FormGCPGood Clinical PracticeGDPRGeneral Data Protection Regulation	
eCRFCase Report FormGCPGood Clinical PracticeGDPRGeneral Data Protection Regulation	
GCPGood Clinical PracticeGDPRGeneral Data Protection Regulation	
GDPR General Data Protection Regulation	
5	
ICF Informed Consent Form	
ISF Investigator site file	
ISRCTN International Standard Randomised Controlled Trials Number	•
LC-MS/MS Liquid chromatography-tandem mass spectrometry	
MS Mass Spectrometry	
MHC Major Histocompatibility Complex	
NHS R&D National Health Service Research & Development	
PBMC Peripheral Blood Mononuclear Cell	
PI Principal Investigator	
PIS Participant Information Sheet	
REC Research Ethics Committee	
SAE Serious Adverse Event	
SLS School of Life Sciences	
SOP Standard Operating Procedures	
TASC Tayside Medical Science Centre	
TBR Tayside Biorepository	
TCTU Tayside Clinical Trials Unit	
TMB Tumour Mutational Burden	
TMF Trial Master File	
TMG Trial Management Group	
TSA Trial Scientific Adviser	

## II. STUDY SUMMARY

Study Title	Proteomic Profiling of Oesc Junction A denocarcinoma	ophageal and Gastroesophageal N eoantigens		
Short title	PROTEAN			
Study Design	Basic science			
Study Participants	Patients with oesophageal or ga adenocarcinomas	stroesophageal junction		
Planned Sample Size	75 (50 oesophageal samples/25	i lower oesophageal-gastric samples)		
Follow up duration	18 weeks			
	Objectives	Outcome Measures		
Primary	To characterise neoantigen profiles of oesophageal or gastroesophageal junction adenocarcinomas	Neoantigen profiles for individual patients with oesophageal or gastroesophageal junction adenocarcinomas		
Secondary	
 
To determine the feasibility of neoantigen profiling using tumour biopsies of oesophageal or gastroesophageal junction adenocarcinomas
 
To identify oesophageal or gastroesophageal junction adenocarcinoma neoantigens as candidate targets for immunotherapy
 
To investigate the relationship between neoantigen profiles and clinical outcomes
 
Recovery of RNA and DNA from samples
 
	
 
Proportion of patients in which neoantigen profiles are successfully generated from biopsies
 
Characterise pre-existing T cell responses to identified neoantigens
 
Correlate objective response rate, disease control rate, progression free survival and overall survival with neoantigen profiles
 
Genomic and transcriptomic studies; neoantigen validation experiments.
 
		

#### III. FUNDING AND SUPPORT IN KIND

FUNDER(S)	FINANCIAL AND NON-FINANCIAL SUPPORT GIVEN
Platinum Informatics,	Funding for the trial.
[name]	Scientific expertise in immunoprecipitation, liquid chromatography-tandem mass spectrometry, and analysis of data to identify tumour neoantigens.

#### IV. ROLE OF STUDY SPONSOR AND FUNDER

The roles and responsibilities of the Sponsor and Funder will be detailed in the Clinical Research Agreement.

### V. ROLES AND RESPONSIBILITIES OF STUDY MANAGEMENT COMMITEES/GROUPS & INDIVIDUALS

The Chief Investigator (CI) will be responsible for the conduct of the study. Site delegate(s) will oversee the study and will be accountable to the CI. A study-specific Delegation Log will be prepared for each Site, detailing the duties of each member of staff working on the study.

The study will be conducted in accordance with the principles of Good Clinical Practice.

In addition to Sponsorship approval, a favourable ethical opinion will be obtained from an appropriate NHS Research Ethics Committee (REC). Appropriate NHS R&D permission(s) will be obtained prior to commencement of the study.

The study will be co-ordinated by a Trial Management Group (TMG), consisting of the CI and Trial manager, other appropriate members will be invited. TMG membership details and minutes of the TMG meetings will be maintained in the Trial Master File (TMF).

#### VIII. STUDY FLOW CHART

\*Treatment can be planned to occur subsequently or recently completed. Eligible participant may be pre-, post- or between treatments.

\*May be by telephone if participant is not attending a standard of care clinic visit.

¥A maximum of 2 additional optional research blood samples and 3 research biopsy samples may be collected. This includes during standard of care procedures at any time during the study period and also research biopsy / PBMC up to 28 days after radiological and/or clinical progression.

## 1. BACKGROUND & RATIONALE

#### 1.1. Immunotherapy in Oesophageal Adenocarcinoma

Clinical outcomes for gastroesophageal adenocarcinomas with standard approaches involving cytotoxic chemotherapy, radiotherapy and surgery have limited effectiveness, with the majority of patients dying within a year of diagnosis, and only 15% surviving 5 years [1]. Immune checkpoint inhibitors have provided durable clinical responses in patients with advanced solid tumours [2]. Recently clinical trials have extended this observation to gastroesophageal adenocarcinomas and established checkpoint inhibitors as a standard of care (see Table 1.1) [3-15]. The durable responses seen to checkpoint inhibitors in advanced stage gastroesophageal adenocarcinomas are hitherto unprecedented and have had a transformative impact on patients in this clinical setting.

However, the majority of gastroesophageal cancer patients are resistant to checkpoint inhibitors and do not benefit [16]. Predictive biomarkers Programmed Death Ligand-1 (PDL1),Tumour mutational burden (TMB) and Microsatellite instability-high (MSI-H), can identify sensitive patients and enrich treated cohorts for those most likely to benefit clinically, but new and alternative immunotherapy strategies are needed to extend the benefits of durable 'immune type' responses to a larger proportion of patients with gastroesophageal adenocarcinoma [16].

The tumour immune microenvironment has been identified as a key factor in determining the outcome of immunotherapies. Immune checkpoint inhibitors show better clinical response in tumours (including oesophageal adenocarcinomas), with high levels of infiltrating T cells together with more antigens, including neoantigens compared to those lacking tumour-reactive infiltrating T cells [17]. A number of studies have focussed on converting immune tumour microenvironments from 'cold' with low levels of T cell infiltration into 'hot' with high levels of infiltrating T cells to enhance sensitivity to immune checkpoint inhibitors [16].

T cell–based immunotherapy has been successfully used to treat human solid cancers including metastatic melanoma where complete, durable tumour regressions have been observed [18-24]. However, in solid tumours broadly, success has been more limited, with durable responses an uncommon occurrence, and this clinical experience has highlighted a number of barriers to the development of effective T cell–based immunotherapy including a limited array of targetable antigens and heterogeneous antigen expression between patients [25]. More recently an early phase trial demonstrated safety and promising efficacy for Chimeric Antigen receptor T-Cell therapy (CART-T) in gastric cancer. In advanced stage gastric cancer patients treated with at least 2 previous lines of treatment including checkpoint inhibitors in 44%, CT041, an anti-CLDN18.2 CAR-T cell therapy, reported objective response rate of 61.1% median progression free survival of 5.4 months and median overall survival 9.5 months [26]. This study provides a proof of concept for the effectiveness of an adoptive T cell-based approach in gastroesophageal adenocarcinoma, importantly including in those patients resistant to checkpoint inhibitors.

Similar challenges have been encountered in clinical studies with cancer vaccines, although recent technological advances with mRNA vaccines provide solutions if suitable targets can be defined [27-30]. Vaccines present tumour-specific antigens and activate cytotoxic T cells to recognise tumour cells and infiltrate into tumours, thereby training the immune system to target

and kill tumour cells, and also convert tumour immune microenvironments from 'cold' into 'hot' which could enhance effectiveness of immune checkpoint inhibitors as well [27-30].

## **1.2. Targeting tumour neoantigens as a therapeutic strategy**

Increasing evidence suggests that T cells specific for tumour neoepitopes (neoantigens) derived from the products of tumour specific gene aberration stimulate a strong cytotoxic T cell– mediated immune response and are important for tumour regression in patients receiving tumour infiltrating lymphocytes (TILs) therapy, and immune checkpoint inhibitors [31-33]. Neoantigen profiles may therefore have value as predictive biomarkers for immune checkpoint inhibitors to guide optimised personalised treatment strategies, for example as either monotherapies or in combination regimens.

Neoantigen-specific T cells generated de novo from tumour-specific somatic mutations, are not subject to central and peripheral tolerance and cannot target normal tissues. Thus, neoantigens represent ideal targets for T cell–based cancer immunotherapy and other therapeutic strategies including cancer vaccines, that harness a T cell response against neoantigens could also significantly benefit cancer patients. Therefore, targeting neo-antigens promises high therapeutic specificity but since in solid tumours, due to between patient genomic heterogeneity they are largely patient-specific, a precision medicine approach may be required built upon neoantigen identification in individual patients. Oesophageal adenocarcinoma has high TMB and high predicted neoantigen loads associated with increased CD8+T cell density, and genomically exhibits high levels of inter-patient heterogeneity [34, 35].

## 1.3. Neoantigen identification

Current methods to identify tumour neo-antigens have a number of limitations and identifying patient specific, individualised, targetable neoantigens remains a major obstacle to neoantigen based therapies for cancer. Neoantigen identification at present mainly involves whole-genome, whole exome, and transcriptome sequencing [36-42]. However systematic immunogenicity assessment of neoepitopes for common driver mutations in solid tumours is currently lacking. Current methods for immunogenic neoantigen identification often require synthesis of dozens to hundreds of peptides and are time-consuming and costly and have low positive rates. Narrowing down the list of potential neoepitopes and reducing the time of the identification process are currently major unresolved clinical challenges.

Direct identification of neoantigens by the analysis of the tumour ligandome using mass spectrometry (MS) offers a number of advantages, for example translational errors and post-translational modifications (found to be more efficient in triggering an immune response), that cannot be predicted by genomic or transcriptomic approaches, but can be characterized by mass spectrometry analysis [43-45]. Recently dissimilarity to the non-mutated proteome has been shown to identify a subset of neoantigens with distinct hydrophobic properties, high likelihood of immunogenicity, and correlation with benefit from immune checkpoint inhibitors [46].

Table 1.1. Practice changing randomised Phase 3 trials with immune checkpoint inhibitors in gastroesophageal adenocarcinoma (adapted from [16])

Trial	Phase	Population	Setting	Agent	Response rate	PFS	OS
>2nd line							
ATTRACTION-2	3	Advanced GOJ or GC	≥2nd	Nivolumab ( n = 330) vs	11% (8–16%)	1.61 m	5.3 m vs 4.1 m (HR
Kang et al. [5]		(n = 493) Asian population	line	placebo ( n = 163)	DCR 40% (34– 46%)	(1.5–2.3)	0.63, P < 0.0001)
KEYNOTE-059 (cohort 1) Fuchs et al. [7]	2	GC/GOJ (n = 259)	≥2nd line	Pembrolizumab (all patients)	12%  PD- L1 + ve 16% PD- L1 -ve 6% DCR 27	2.0 m (2.0– 2.1)	5.5 m (4.2–6.5)
CHECKMATE- 032 Janjigian et al. [12]	1/2	Advanced OC, GOJ or GC ( n = 160)	≥2nd line	Nivolumab 3 mg/kg (n = 59) nivolumab 1 mg/kg + Ipilimumab 3 mg/kg (n = 49) nivolumab 3 mg/kg + Ipilimumab 1 mg/kg (n = 52)	12% vs 24% vs 8%	12 month: 8% vs 17% vs 10%	12 month: 39% vs 35% vs 24%
JAVELIN-300 Bang et al. [13]	3	GOJ ( n = 111) or GC ( n = 260)	3rd line	Avelumab vs TPC	2.2% vs 4.3% DCR 22.2 vs 44.1%	1.4 m vs 2.7 m	4.6 m vs 5.0 m (HR 1.1, NS)
2nd line							
KEYNOTE-061 Shitara et al. [6]	3	GOJ ( n = 185) or GC ( n = 407)	2nd line	Pembrolizumab (n = 296) vs paclitaxel (n = 296)	CPS ≥ 1: 16% vs 14% CPS ≥ 10: 24.5% v 9.1% CPS < 1: 2% vs 10.4%	1.5 m vs 4.1 m (HR 1.27) CPS < 1: HR 2.05	9.1 m vs 8.3 m (HR 0.82, P = 0.0421) CPS ≥ 10: 10.4 m v 8.0 m (HR 0.64) CPS < 1: 4.8 m vs 8.2 m (HR 1.20)
KEYNOTE-181 Kojima et al. [14]	3	Advanced OAC ( n = 227) or OSCC ( n = 401)	2nd line	Pembrolizumab vs TPC	-	-	ITT: 7.1 m vs 7.1 m SCC: 8.2 m vs 7.1 m CPS > 10: 9.3 m vs 6.7 m

Trial	Phase	Population	Setting	Agent	Response rate	PFS	OS
1st line		•	•		·	•	
KEYNOTE-062 Shitara et al. [15]	3	GC/GOJ (PD-L1 CPS ≥ 1%)	1st line	Pembrolizumab (P) ( n = 256) pembrolizumab + chemotherapy (P + CTx) ( n = 257) chemotherapy (CTx) ( n = 250)	P v CTx: 14.8% vs 37.2% CPS ≥ 10: 25.0% vs 37.8%	P v CTx CPS ≥ 1: 2.0 m v 6.4 m (HR 1.66), CPS ≥ 10: 2.9 m v 6.1 m (HR 1.10)	P v CTx ITT: 12.5 m v 11.1 m (HR 0.85) CPS ≥ 1: 10.6 m v 11.1 m (HR 0.91) CPS ≥ 10: 17.4 m vs 10.8 m (HR 0.69)
ATTRACTION-4 Boku et al. [8]	2	GC/GOJ (n = 724)	1st line	Nivolumab (n = 362)+CTx (SOX/CapOX) vs CTx alone (n = 362)	58% vs 48%	10.5 vs 8.4 (HR 0.68)	17.5 m vs 17.2 (HR 0.90)
KEYNOTE-590 Kato et al. [9]	3	OAC or OSCC ( n = 749)	1st line	Chemotherapy + /pembrolizumab	OSCC: 45% vs 29.3%	-	OSCC (all): 12.6 m vs 9.8 m (HR 0.72) OSCC (CPS ≥ 10): 13.9 m vs 8.8 m (HR 0.57) ITT 12.4 m vs 9.8 m
CHECKMATE 649 Janjigian et al. [3]	3	GC/GOJ ( n = 1266, including Ipilimumab/nivolumab arm)	1st line	Nivolumab+chemotherapy (n = 473) chemotherapy alone (n = 482)	CPS > 5: 60% vs 45%	CPS ≥ 5: 7.7 m vs 6.0 m (HR 0.68)	CPS ≥ 5: 14.4 m vs 11.1 m (HR 0.71, P < 0.0001)

DCR disease control rate; PFS progression free survival; OS overall survival; HR hazard ratio; NS non-significant; m month; SOX S-1/oxaliplatin; CapOx capecitabine/oxaliplatin; GOJ gastroesophageal junctional; GC gastric cancer; OAC oesophageal adenocarcinoma; OSCC oesophageal squamous cell carcinoma; PD-L1 programmed death ligand 1; TPC treatment of physician's choice; CPS combined positivity score.

## 2. OBJECTIVES AND OUTCOME MEASURES/ENDPOINTS

The aims of this study are to characterise neoantigen profiles in oesophageal and gastroesophageal adenocarcinomas and to generate neoantigen profiles for individual patient tumours. This will be achieved by analysing the Major Histocompatibility Complex (MHC) - associated 'immunopeptidome', using a state-of-the-art liquid chromatography-tandem mass spectrometry (LC-MS/MS) based method for direct neoantigen identification. Proprietary software tool DESIMAL, created by Platinum Informatics Ltd. will underpin this work and establish an automated pipeline for raw MS data processing and downstream data interpretation. This study will determine the feasibility of neoantigen identification using this approach in gastroesophageal adenocarcinoma patients, using routinely available clinical biopsy materials. The study will evaluate neoantigens as therapeutic targets for individualised adoptive T cell and/or cancer vaccine approaches for the treatment of oesophageal adenocarcinoma. Additional objectives include the characterisation of pre-existing T cell responses to identified neoantigens and the recovery of RNA and DNA from samples that will be used for genomic and transcriptomic studies and for neoantigen validation experiments.

#### 2.1. Table of endpoints/outcomes

Primary Objective:	Outcome Measure:	Timepoint
To characterise neoantigen profiles of oesophageal or gastroesophageal junction adenocarcinomas	Neoantigen profiles for individual patients with oesophageal or gastroesophageal junction adenocarcinomas	End of study

Secondary Objectives	Outcome Measures	Timepoint	
1- To determine the feasibility of neoantigen profiling using tumour biopsies of oesophageal or gastroesophageal junction adenocarcinomas	
 
Proportion of patients in which neoantigen profiles are successfully generated
 
	1- End of study	
2- To identify oesophageal or gastroesophageal junction adenocarcinoma neoantigens as candidate targets for immunotherapy	
 
Characterise pre-existing
 
T cell responses to
 
identified neoantigens
 
	2- End of study	
3- To investigate the relationship between neoantigen profiles and clinical outcomes	3- Correlate objective response rate, disease control rate, progression free survival and overall survival with neoantigen profiles.	3- End of study	
4- Recovery of RNA and DNA from samples	
 
Genomic and transcriptomic studies; neoantigen validation experiments.
 
	4- End of study	

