## 6.5. Long term follow-up assessments

Nil

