## 6.9. End of study

The end of study at all sites is defined as last participant last visit. The Sponsor, CI and/or the TMG have the right to terminate the study at any time for clinical or administrative reasons.

The end of the study will be reported to the Sponsor, REC and NHS R&D Office(s) within 90 days, or 15 days if the study is terminated prematurely.

A final clinical study report will be published within 1 year of the end of study and will also be provided to the Sponsor and REC.

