## 9.2. Planned recruitment rate

75 participants over 12 months.

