## 9.3.2. Secondary outcome analysis

The feasibility of neoantigen identification with the described approach in gastroesophageal adenocarcinoma patients, using routinely available clinical biopsy materials will be evaluated by assessing the proportion of patients in whom neoantigens are identified. The minimal amount of oesophageal adenocarcinoma tissue, and the qualitative and quantitative histological features associated with successful neoantigen identification will be evaluated to provide data on the features of optimal tumour specimens for future trials. Characterisation of pre-existing T cell responses to identified neoantigens will enhance evaluation of their potential utility as therapeutic targets for adoptive T cell and/or cancer vaccine approaches for the treatment of oesophageal adenocarcinoma. An exploratory analysis of the relationship between tumour neoantigen profiles and objective response rate, progression free and overall survival will be undertaken.

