#### 15.2.2. Data management

Data management will be overseen by TCTU Data Management Team (DMT).

Local sites will be expected to enter data directly on to the eCRF. After data entry, site staff will be expected to visually verify data entered. Worksheets will be provided to facilitate this process, but their use is not mandatory. Worksheets, where used, will not record source data and will not be archived.

All data from participants should be entered on the eCRF within 14 days of the last data collection point for that participant, data entry out with this timeline will not constitute a breach.

Data queries will be generated by the DMT and emailed to sites, return of queries should be within 2 weeks, return of queries out with this timeline will not constitute a breach.

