## 15.4. Appendix 4 – Schedule of Procedures

Visits				
V1 a	V2ª	V3 bc	V4 bc	V5 b
Screening	Day 1 Up to 28 days post screening	Week 6 +/- 7 days	Week 12 +/- 7 days	Week 18 +/- 7 days
Х				
Х				
Х				
Х				
Х				
Х	х	Х	Х	Х
	х			
		X A maximum of 3 further research biopsy samples may be collected between day 1 and week 18		ected
	х			Х
		X A maximum of 2 further research blood samples may be collected between day 1 and week 18		
	Х	Х	Х	Х
	х	Х	Х	Х
	V1 a Screening X X X X X X X X	V1aV2aScreeningDay 1Up to 28 days post screeningXX	V1aV2aV3bcScreeningDay 1 Up to 28 days post screeningWeek 6 +/- 7 daysXX	V1aV2aV3bcV4bcScreeningDay 1 Up to 28 days post screeningWeek 6 +/- 7 daysWeek 12 +/- 7 daysXImage: ScreeningXImage: ScreeningXImage: ScreeningImage: ScreeningImage: ScreeningXImage: ScreeningImage: ScreeningI

a Visits 1 & 2 may be combined

b Visits will be conducted at the same time as standard care procedures and may not fall in line with visit windows, this will not be considered a breach.

c May be by telephone if participant is not attending a standard care clinic visit.

Activity	Responsibility	Timing	Comments
Review for AEs	Trial staff	Each visit	Recorded on eCRF
			system.
Review of recorded	PI (or delegate)	Within 10 days of	Recorded on eCRF
AEs for relatedness		recording	and/or medical
and seriousness			records.
Reporting SAEs:	PI (or delegate)	Within 10 days of	SAE form:
All SAEs need to be		becoming aware of	Non-CTIMP safety
assessed by the PI		SAE	report
or delegated doctor.			Report to:
			CI
			TCTU Trial Manager
Reporting SAEs:	CI	Within 15 days of PI	Report to:
All SAEs need to be	TCTU Trial Manager	becoming aware of	REC
signed off by the CI.		SAE	Sponsor

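### Overall survival is listed at end of study, but each participant's data collection stops at week 18, so later deaths already in the medical records are not collected

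*Protocol*

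**What the plan says.** Section 2.1 of the protocol sets the outcome measure for secondary objective 3 as "Correlate objective response rate, disease control rate, progression free survival and overall survival with neoantigen profiles", and the timepoint beside it is end of study. Section 9.3.2 describes the work as exploratory: "An exploratory analysis of the relationship between tumour neoantigen profiles and objective response rate, progression free and overall survival will be undertaken".

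Other sections fix how long data are collected:

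- The study summary gives a follow-up duration of 18 weeks.
- Appendix 4 ends at visit 5, week 18 plus or minus 7 days. A footnote allows slippage: "Visits will be conducted at the same time as standard care procedures and may not fall in line with visit windows".
- Section 6.5, "Long term follow-up assessments", has the single entry Nil.
- Section 15.2.2 closes data entry person by person: "All data from participants should be entered on the eCRF within 14 days of the last data collection point for that participant".
- Section 9.2 plans "75 participants over 12 months".
- Section 6.9 states: "The end of study at all sites is defined as last participant last visit".

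Section 10.1 makes medical records the source data, and section 12.10 says the local cancer service continues to follow participants up.

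**The concern.** The timepoint in section 2.1 and the collection schedule do not match. If end of study means status at that date for everyone, nothing in the schedule, section 6.5 or the data-entry rule provides for obtaining it. If it means week 18, the label does not tell the reader that survival is censored there.

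The window is also short for this disease. Section 1.1 speaks of "the majority of patients dying within a year of diagnosis", and 18 weeks is about 4.1 months. Deaths after week 18 among early enrolees will be in records the sites already hold, yet the plan asks nobody to extract them. No analysis plan can recover dates that were never collected. At stake is how much the exploratory comparison of neoantigen profiles with survival can show beyond early death.

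**Working it through.** **The plan's own figure.** There is none to reproduce. Section 9.1 says a formal sample size calculation is not possible, and no event target is given.

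**Inputs from the protocol.** N = 75; accrual A = 12 months (section 9.2); follow-up f = 18 weeks = 18 × 7 / 30.4375 = 4.14 months (study summary); study end at A + f = 16.14 months after first enrolment (section 6.9). Median survival values are taken from across Table 1.1, plus 12 months as a base case suggested by section 1.1.

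**Assumptions, not in the protocol.** Survival is exponential from enrolment, accrual is uniform, all 75 are profiled, and there are no withdrawals.

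**Formulas**, with L = ln 2 / median:

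- Deaths by week 18 = N × (1 − exp(−L f))
- Deaths by study end = N × {1 − [exp(−L f) − exp(−L (f + A))] / (L A)}
- Share outside the window = 1 − (first / second)

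**Median 12 months, worked.** L = 0.0578. By week 18: 75 × (1 − 0.787) = 16.0. By study end: 75 × {1 − [0.787 − 0.394] / 0.693} = 32.4. Share outside: 51%.

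| Median survival (months) | Deaths by week 18 | Deaths by study end | Share outside window |
|---|---|---|---|
| 4.1 | 37.8 | 59.1 | 36% |
| 5.3 | 31.4 | 53.0 | 41% |
| 7.1 | 24.9 | 45.5 | 45% |
| 9.1 | 20.3 | 39.1 | 48% |
| 12 | 16.0 | 32.4 | 51% |
| 14.4 | 13.5 | 28.3 | 52% |
| 17.5 | 11.3 | 24.3 | 53% |

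**Sensitivity at a 12-month median.** Accrual over 6, 18 or 24 months gives 36%, 58% or 63%. A Weibull shape of 0.7, 1.3 or 1.5 gives 38%, 62% or 68%. The share does not depend on N: fewer profiled participants lower both counts in proportion.

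**Progression-free survival, same formulas, medians from Table 1.1.**

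| Median PFS (months) | Events by week 18 | Events by study end | Share outside window |
|---|---|---|---|
| 1.5 | 63.9 | 73.0 | 12% |
| 4.1 | 37.8 | 59.1 | 36% |
| 7.7 | 23.3 | 43.4 | 46% |
| 10.5 | 17.9 | 35.6 | 50% |

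**The case against.** The strongest reply is that the protocol calls this analysis exploratory, describes the primary outcome as qualitative (section 9.3.1) and claims no power for survival. Judging it against a power target would be unfair. That stands, and it bounds the importance of the point. It does not explain why dates bearing on a stated objective should go uncollected when the sites hold them.

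The size is also uncertain. The statement in section 1.1 runs from diagnosis, whereas my clock runs from enrolment. Participants may enter before, between or after treatments, and eligibility has no stage limit, so the true median could be shorter or longer. At the later-line medians of 4.1 to 5.3 months, week 18 alone would yield about 31 to 38 deaths. Section 9.5 removes failed samples from the profile analysis, so 75 is optimistic for the counts.

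Finally, the end-of-study timepoint, with medical records as source data, could be read as survival status taken at study end. That reading is possible, but no procedure carries it out.

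A reader might infer several stronger things that the documents do not support:

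- That half the deaths are lost, as a fact. This is a modelled figure and drops to 36-41% at the shorter medians.
- That data are thrown away. They are simply not collected.
- That progression-free survival suffers equally. With short medians, most events fall inside 18 weeks.
- That only a handful of deaths would be seen. The table gives 11 to 38.

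**Conclusion.** The point holds as a mismatch between the stated timepoint and the collection schedule, with a real but uncertain loss of information on overall survival. Under the assumptions above, deaths by study end that go uncollected are about 36-41% of the total at medians of 4-5 months and 45-53% at 7-18 months. For progression-free survival the loss is about 12% at a median of 1.5 months and 46% at 7.7 months.

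This limits one exploratory secondary analysis. It does not touch the primary outcome or the feasibility estimate. Nor would collecting the later deaths make the survival analysis confirmatory: about 32 deaths at a 12-month median still supports only exploratory estimation. The case for change is that the gain is cheap.

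**What to change.** In section 6.5 and Appendix 4, add one record-based extraction at last participant last visit for every participant who has not withdrawn: vital status, date of death and date last known alive. Censor overall survival at that common date, or at the date last known alive if earlier. Adjust the data-entry rule in section 15.2.2 to allow this late entry. Leaving out withdrawn participants respects section 6.7, which bars further collection after withdrawal.

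Progression dates after week 18 may be extracted too. Mark them as routinely documented and keep them distinguishable from the RECIST v1.1 assessments up to week 18 (section 6.4), because routine notes may not apply the same criteria.

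If the sponsor prefers not to extend collection, relabel the outcomes as overall survival and progression-free survival censored at 18 weeks, and reconcile section 2.1 with the study summary, section 6.5 and Appendix 4.

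The cost is an amendment, a line in the information sheet and one look-up per participant, with no added visit or procedure. Sites that finish early would stay open for that last entry. Section 9.3 already delays outcome analysis until all samples are collected and the mass spectrometry is complete, so little delay should follow.
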